6.4 Visit 5 – 12 months/Final Assessment

A final Assessment Visit will be completed for all participants at completion of the study or earlier if required.

The following assessments are expected to be conducted in clinic and must be recorded in the CRF:

- Adverse Events
- Any exacerbations of COPD
- Any changes in concomitant medications
- Pregnancy and contraceptive review (if there is concern of pregnancy, another pregnancy test will be administered)
- Vital signs
- Blood analysis (Biochemistry)
- Sputum collection
- ECG
- ICAM-1 collection
- Adherence to study treatment
- Spirometry
- SGRQ-C assessments
- COPD Assessment Tool (CAT)
- Modified MRC breathless score

- Return of unused study medication and accountability
- Study medication adherence and accountability

6.5 Exacerbation visits

All reported moderate and severe COPD exacerbations that occur from washout until the study medication has stopped and the final safety assessment call completed should be recorded in the database. The data required includes

- Symptom start Date
- Symptom resolution date;
- increase in sputum
- change in colour of sputum
- worsening cough
- worsening breathlessness
- antibiotics or oral steroids prescribed.
- Watch out for signs of pneumonia: e.g., crepitations/bronchial breathing on auscultation and if so then proceed to do perform a chest x-ray to confirm or refuse radiological presence or absence of pneumonia.

Any medications prescribed should be recorded in the exacerbation medication log.

Patients commencing washout will be given an Exacerbation Diary and asked to record and report to the local study team any exacerbations that occur throughout the duration of the study period. They will be asked to record details of each episode, including what treatments were received (in the exacerbation medication log) and any change in symptoms for a period of 2 weeks (or until they report they are well again). They will be advised to bring this with them to each follow-up visit. These will be checked against any other reported exacerbations.

Patients will be advised to contact a member of the study team to inform them if they develop worsening symptoms of their COPD. A clinical decision will be made whether the patient needs to attend for a visit for further investigation to rule out pneumonia.

Reports of exacerbations may come from a variety of sources patients; GP'S, clinic visits, hospital admissions.

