Pneumonia in patients with COPD Systemic effects of corticosteroids: bone disorders,	Pneumonia is a class concern for any ICS-containing product for the treatment of COPD. In two replicate 12-month studies, in the FF/VI clinical program, in a total of 3,255 patients with COPD who had experienced a COPD exacerbation in the previous year, there was a higher incidence of pneumonia (6%-7%) reported in patients receiving the FF (at strengths of 50, 100, and 200 µg)/VI 25 µg combination than in those receiving VI 25 µg alone (3%). In some instances, these pneumonia events were fatal (including one fatality on FF/VI 100/25 µg dose). Risk factors for pneumonia observed in these studies included current smokers, patients with a history of prior pneumonia, patients with a body mass index <25 kg/m2 and patients with an FEV1<50% predicted. These factors should be taken into consideration when using an ICS in patients with COPD with coexistent bronchiectasis. Pneumonia risk will be important in the benefit-risk assessment for FF/UMEC/VI in COPD patients, hence a robust risk mitigation strategy is being proposed. A decrease in bone mineral density and the risk of fractures is a class	 the protocol (section 3.5) Collection of information on previous history of pneumonia in past 12 months, including hospitalisation at baseline Use of pneumonia electronic Case Report Form (eCRF) All diagnoses of pneumonia (radiographically confirmed or unconfirmed) must be reported as an AE or SAE (if applicable) CXR read required whenever a patient has suspected pneumonia
bone mineral density decrease and associated fractures	and the risk of fractures is a class concern for any ICS-containing product for the treatment of COPD. This is however a very small risk as has been shown in previous studies.	bone systemic corticosteroid effects will be conducted through assessment of reported bone adverse events (Review AE/SAE reports)

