4.7.3 Restricted Medications

Restricted medications are those that, in the opinion of the Investigators, could result in changes to the airway and lung bacteriology and microbiome that are not the result of the investigational treatment. Patients receiving local or systemic antibiotic treatments, or local corticosteroids e.g., nasal corticosteroids at baseline would exclude participation in the study.

Patients having an exacerbation requiring antibiotics or corticosteroids during the study period (after randomisation) will attend for an unscheduled visit if deemed necessary by the investigator team. Participants with a potential exacerbation of COPD or wishing to withdraw for any other reason during the washout phase will be offered a visit for clinical assessment by the study team.

Restricted medications therefore would be

- Nasal corticosteroid spray
- Antibiotics of any sort unless being administered for a COPD exacerbation

If restricted medications are commenced for clinical reasons the patient may continue in the study and continue to take IMP, but the trial manager should be notified that a restricted medication has been commenced, and this should be recorded in the CRF.

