4.7.4 Prohibited Medications

Corticosteroids

Inhaled corticosteroids of any class should not be commenced during the study other than those provided as part of the study Systemic corticosteroids should not be commenced for the treatment of stable COPD during the study, unless in the "oral prednisolone" arm of the study at the end.

If systemic corticosteroids are commenced for the treatment of acute exacerbation of COPD, this should be recorded and the patient should attend for an exacerbation visit.

Systemic antibiotics:
Penicillin
Tetracycline
Other antibiotics

Patients should not commence long-term antibiotic therapy for COPD during the study period. Only exception is if they have been on long-term macrolides for more than 3 months; this will be allowed to continue. Antibiotics may be administered for the treatment of an acute exacerbation, but this should be recorded, and the patient should attend for an exacerbation visit.

Roflumilast ritonavir, itraconazole, telithromycin, or ketoconazole.

These are anti-inflammatory medications that could theoretically affect the airway microbiome by modulating the immune system.

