5.3 STUDY ASSESSMENTS

Investigations (A	All Patients)	Screening and Consenting Visit	Medication Washout Period 4 weeks	Baseline/Randomisation	Telephone Follow-up contact	Month 6 +/- 2 Weeks	Month 12 or Final Assessment +/- 3 Weeks			Exacerbation Visit (Face to face or telephone visits)
Visit Number		Visit 1		Visit 2	Visit 3	Visit 4	Visit 5	Visit 6 *	Visit 7	As necessary
Time relative to	randomisation	- 4w	-4w	0	1m + 2d	6m	12m	1 to 12m	12m + 7d	1 to 12
Time window fo	or evaluation	N/A	N/A	4 weeks ±2 days from screening		+ 2 weeks from randomisation	+ 3 weeks	+2d	+3d	-
Written Informe		✓								
LMP, Pregnancy review (where a	Test & Contraception applicable)	✓		√		✓	✓		✓	
Physical Examin and weight)	ation (including height	✓								✓
Current COPD M	ledications?	✓		✓	✓	✓	✓	✓	✓	✓
Concomitant Me	edications	✓								
Past Medical His	story?	✓								
Demographics		✓								
Stratification				✓						
Lifestyle		✓								
Eligibility review		✓		✓						
Reaffirm Conser				✓		✓	✓		✓	✓
Medication Was	hout & Accountability			✓						
Randomisation				✓						
Spontaneous Sputum	Sputum Colour			✓		✓	✓		✓	
Sputum	Qualitative and Quantitative Microbiology 16S RNA Pyrosequencing			√		√	✓			
Sputum inflammatory assays	Myeloperoxidase (MPO) Free elastase activity			✓		· ·	✓		- v	

Routine Bloods	FBC including								
tests	eosinophil count,				✓	√		1	
	CRP, ICAM-1		ľ		•	•		•	
	U&E's, LFT's								
	Fibrinogen								
Spirometry	FEV1 + FVC;								
	FEV1/FVC; mid	✓	✓		✓	✓		✓	
	expiratory flows								
	(FEF25-75)								
Questionnaires	COPD Assessment								
	Tool		 		✓	✓		✓	✓
	St George's		·		·				
	Respiratory SGRQ-C								
	eathlessness score	✓	✓		✓	✓		✓	
12 Lead ECG		✓			✓	✓		✓	
Vital signs (Pulse, respiratory rate,									
blood pressure, oxygen saturations on		✓	✓		✓	✓		✓	✓
room air and body temperature)									
Exacerbations (Number of and time to			✓	✓	✓	,	✓	√	
1st moderate/sev	vere exacerbation)		V		v	✓		•	
Collection of all AE and SAE data (as in			,	✓	,	,	✓	,	,
section 11)	section 11)		✓		✓	✓		✓	✓
Dispense randomised study			✓		✓				
Medication?									
Study Medication	Study Medication Adherence (&			✓	✓	✓		✓	✓
Accountability check if face to face)									
	,					✓			
						,			
						✓			
								✓	✓

Table 1 of assessments

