4.5.8 Exacerbations

Table showing the number and percent of participants with radiologically confirmed pneumonia split by treatment allocation.

Descriptive analysis split by treatment allocation, of:

- number of exacerbations requiring treatment with antibiotics and or steroids
- number of exacerbations requiring treatment with antibiotics and or steroids that also includes hospitalisation

A Kaplan-Meier survival curve stratified by treatment allocation will be presented along with the accompanying log-rank statistic for the time to first moderate or severe exacerbation where this is defined as an exacerbation requiring treatment with antibiotics and or steroids.

Version No 2.1

Effective Date 27Jun2025

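### The Protocol contradicts itself on whether a treated exacerbation must be attended, so in this open-label trial detection of the pneumonia safety endpoint may differ by arm

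*Protocol*

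**What the plan says.** **Attendance.** Protocol 4.7.4 covers both treatments for an acute exacerbation. For systemic corticosteroids, "this should be recorded and the patient should attend for an exacerbation visit". For antibiotics: "Antibiotics may be administered for the treatment of an acute exacerbation, but this should be recorded, and the patient should attend for an exacerbation visit". Protocol 4.7.3, on the same kind of event after randomisation, says that patients "will attend for an unscheduled visit if deemed necessary by the investigator team". Protocol 6.5 says: "A clinical decision will be made whether the patient needs to attend for a visit for further investigation to rule out pneumonia". The Table 1 column is labelled "Exacerbation Visit (Face to face or telephone visits", so a call counts as a visit.

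**Chest X-ray.** The pneumonia row of the risk table in Protocol 4.5 states: "CXR read required whenever a patient has suspected pneumonia". Protocol 6.5 tells staff to look for signs of pneumonia, gives auscultation findings as examples, and orders an X-ray if they are present.

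**Collection.** Protocol 4.5 requires every pneumonia diagnosis, with or without radiographic confirmation, to be reported as an AE or SAE, and refers to a pneumonia eCRF. Protocol 9.3.3 collects community-diagnosed pneumonia whatever its severity or seriousness.

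**Analysis.** Protocol 2.2.2 defines the endpoint as participants with radiologically confirmed pneumonia. SAP 4.5.8 follows it: "Table showing the number and percent of participants with radiologically confirmed pneumonia split by treatment allocation". No test is named. SAP 4.6 gives overall AE/SAE counts and a line listing of SAEs only.

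**Blinding.** SAP 4.9 says that participants and the treating team know the allocation and that the microbiology staff do not. Neither document describes blinded or central reading of chest X-rays.

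**The concern.** Protocol 1.1 calls pneumonia the main reported risk of inhaled corticosteroids in COPD, and 1.2 gives it as a reason for studying this population. A case enters the pneumonia table only if it was imaged, and imaging usually depends on the patient having been seen. With two attendance rules in force, two sites, or one site with two similar patients, can act differently and both comply. Where the judgement is made by people who know the allocation and expect pneumonia with the steroid, the chance of confirmation could depend on the arm.

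At stake is whether a pneumonia difference, or its absence, can be read as an effect of treatment. No planned output shows how often exacerbations were seen or X-rayed, so the reader could not judge. Protocol 3.2 also has the DMC review the safety endpoints when it considers stopping.

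**Working it through.** **1. The attendance passages side by side**

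| Place in Protocol | Patient | Rule |
|---|---|---|
| 4.7.4 | Given systemic steroids or antibiotics for an exacerbation | Should attend an exacerbation visit |
| 4.7.3 | Exacerbation needing antibiotics or corticosteroids, after randomisation | Attends if the investigators think it necessary |
| 6.5 | Reports worsening COPD | Attendance is a clinical decision |
| 5.3, Table 1 | Exacerbation visit | Face to face or telephone |

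The first two rows describe the same patients and give different rules. That is a direct conflict.

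**2. The X-ray passages.** These can be read together: the signs in 6.5 are examples of what raises suspicion, and 4.5 requires a film once there is suspicion. What remains is practical. A telephone visit cannot produce the auscultation signs that 6.5 names, so after a call the route to an X-ray runs through the discretionary decision to bring the patient in.

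**3. Where each kind of case appears in the SAP**
- Confirmed: its own table (4.5.8).
- Unconfirmed and serious: pooled counts and the SAE line listing (4.6).
- Unconfirmed and not serious, including community-diagnosed: pooled AE counts only, not identifiable as pneumonia.

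**4. Number per arm.** Protocol 8.1: difference 0.76, SD 0.98, two-sided 5%, 90% power. Normal approximation: n = 2 × (1.960 + 1.282)² × 0.98² / 0.76² = 34.9, so 35. The noncentral t gives power 0.892 at 35 and 0.901 at 36, so the stated 36 is reproduced; 36 / 0.90 = 40. The documents give no sample size or power for pneumonia.

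**5. Expected pneumonia counts.** Protocol 4.5 cites 12-month studies with 3% on vilanterol alone and 6-7% with fluticasone furoate added. Carrying these rates over to the two arms is an assumption.
- Dual: 40 × 0.03 = 1.2
- Triple: 40 × 0.06 = 2.4, to 40 × 0.07 = 2.8
- Ratio: 2.0 to 2.3

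Two-proportion power at 40 per arm is about 9% (3% v 6%) to 13% (3% v 7%); 80% power would need about 749 or 465 per arm. The comparison can only be descriptive.

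**6. Effect of unequal confirmation.** Expected confirmed cases = 40 × true risk × probability of confirmation. The confirmation probabilities are assumptions, used in both directions.

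| True risk, dual v triple | Confirmed, dual v triple | Expected cases | Ratio, triple/dual |
|---|---|---|---|
| 3% v 6-7% | any equal value | – | 2.0-2.3 |
| 3% v 6-7% | 50% v 90% | 0.60 v 2.16-2.52 | 3.6-4.2 |
| 3% v 6-7% | 90% v 50% | 1.08 v 1.20-1.40 | 1.1-1.3 |
| 6.5% in both | 50% v 90% | 1.30 v 2.34 | 1.8 |
| 6.5% in both | 90% v 50% | 2.34 v 1.30 | 0.56 |

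With equal true risk the ratio is that of the confirmation probabilities, whatever the risk: at 15% in both arms the counts are 3.0 v 5.4 and the ratio is again 1.8. A true excess would vanish if confirmation in the triple arm were 3/6 = 0.50 to 3/7 = 0.43 of that in the dual arm.

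**The case against.** The strongest reply is that this is one loose attendance instruction around a descriptive secondary count in a proof-of-concept trial. Several parts of it stand.

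- A reader might infer that the SAP conflicts with the Protocol. It does not: the SAP has no attendance or X-ray rule, and its table matches the Protocol endpoint.
- A reader might infer two incompatible X-ray rules. The examples in 6.5 do not support that.
- A reader might infer that triple-arm patients will be called in more often and that a false steroid signal will follow. Nothing in the documents establishes occurrence or direction. Protocol 1.2 promises careful monitoring of dual-arm patients, which could raise detection there.
- A reader might infer that unconfirmed cases are lost. They must be reported, reports may come from GPs and hospital admissions, and serious cases are listed individually. Only the non-serious unconfirmed ones cannot be identified in a planned table.
- The pneumonia eCRF is not reproduced, and some row labels of Table 1 are missing from the text available here, so useful fields may already exist.
- A clinician's unconfirmed diagnosis is more subjective than a film, and a single rule would not blind anyone.

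The attendance conflict could be narrowed by letting a telephone call count as the visit and confining discretion to in-person investigation. That fits the verb attend poorly, and a site should not have to infer it. The reply therefore limits the size of the point but does not remove it.

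**Conclusion.** The Protocol's rules on attending a treated exacerbation conflict and should be reconciled. Because the trial is open label and the only pneumonia-specific table requires radiological confirmation, detection of this safety endpoint may differ by arm, in either direction. That is a risk created by the design and wording, not something the documents show to have happened.

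With about 1.2 against 2.4-2.8 participants expected, one or two undetected cases would change the picture. This rests on applying the cited rates to this population, whose bronchiectasis may give a different risk; the confirmation probabilities in the illustration have no source. The CFU primary endpoint is not touched. This is an inexpensive improvement that makes the safety comparison interpretable.

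**What to change.** 1. **Protocol.** Reconcile 4.5, 4.7.3, 4.7.4, 6.5 and Table 1 so that sites follow one consistent attendance and X-ray rule in both arms, and state how a telephone visit fits it. The clinical rule is for the sponsor to choose.
2. **SAP 4.5.8.** Keep radiologically confirmed pneumonia as the endpoint and add, by arm:
   - (a) participants with any pneumonia diagnosis, confirmed or not, including community-diagnosed, as a supportive row, with a note that it is more subjective in an open-label trial;
   - (b) the number and share of treated exacerbations seen face to face, and the number and share X-rayed.
3. **Data.** Take (b) from the exacerbation and pneumonia eCRFs where the fields exist, and add fields only where they do not. Row (a) uses diagnoses that must already be reported.
4. **Interpretation.** State in the SAP that any pneumonia difference, or lack of one, will be read in the light of (b).

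**Cost.** Two table rows and possibly a few form fields. Data for (b) may be incomplete for exacerbations already recorded, and the extent should be reported. Depending on the rule chosen, there may be more visits or X-rays.

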6.6 Visits 3 and 6* - Safety Follow-up Telephone Calls

A member of the research team will telephone the participant and document:

- 1 month post randomisation to review their adherence to the study medications: check for any exacerbations (as specified in secondary endpoints in section 2.2) and ask about any AEs/SAEs
- 7 days (+3d) from end of all study medication to check for any SAE's or exacerbations. This will be recorded on the eCRF.

6.7 CASE REPORT FORMS

Data will be collected using electronic case report forms (eCRF) via the secure web interface to the trial database.). The data that will be collected by each eCRF are listed below at each time point.

Identifiable data will not be recorded on the eCRF until after consent has been obtained.

All consented participants will be entered into the eCRF.

Those who do not satisfy the washout period compliance (taken at least 50% of washout medication) will be logged as a screen fail in the eCRF.

6.8 SOURCE DATA COLLECTION

Source data is defined as all information in original records and certified copies of original records or clinical findings, observations, or other activities in a clinical trial necessary for the reconstruction and evaluation of the trial. Source data are contained in source documents.

Source documents are original documents, data and records where source data are recorded for the first

The Investigator will maintain source documents for each patient in the study, consisting of case and visit notes (hospital or clinic medical records) containing demographic and medical information, laboratory data, electrocardiograms, and the results of any other tests or assessments. All information relevant to a participant's general medical history on CRFs must be traceable to these source documents in the patient's case notes. The CRF will be used as source data unless otherwise detailed in the source data plan.

Source data for each critical data point will be documented in a site level source data plan.

6.9 TRIAL DATABASE

A secure trial database will be provided using REDCap and maintained by the Edinburgh clinical Trials Unit. A bespoke randomisation system will be built to manage the randomisation and allocation of IMP. Medication will be automatically assigned once randomised through the randomisation system. This will be linked to REDCap via the REDCap Application Programming Interface (API). Access to the database is role based and site users are restricted to access their own site data only. Trained and delegated members of the study team will be given password-protected logins to the database to complete data entry. All users will require training before access is granted.

The TM and ECTU will provide support for users during working hours. The database will have a secure audit trail and back-up procedures to minimise potential data loss.

Local research staff delegated to do so on the delegation log will enter all trial data into the trial database using eCRF's. Data entry errors will be minimised by using range, completeness and consistency validation checks. REDCap provides the facility for sites to download and print PDFs of the participant's entered data.

The unblinded trial statistician will be given 'read only' access to the database.

Data will be stored on secure servers hosted by the University of Edinburgh that require user authentication, archived after the end of the trial, and made available in de-identified format to satisfy data sharing requirements at the end of the trial.

7. DATA MANAGEMENT

7.1 Personal Data

Demographic, clinical, and personal data will be collected as part of the research, as described

Personal data will be stored by the local research study team on NHS computers (desktop and laptop). Computers will be password protected and kept in locked offices. All local paper files containing personal data will be held in filing cabinets in NHS offices that will be locked when unattended. Access to the study documents will be by the study team only.

7.2 Transfer of Data

Participants are informed about the need for the trial to share data to the following sources, which involves transfer of their personal data to ensure that they are identified correctly: sources such as the participant's general practitioner; hospitals involved in TEMPESTAS.

Participants consent to the use of information about them to support other research in the future, and that the information may be shared anonymously with other researchers, whatever happens to the participant.

Data Transfer will be in accordance with General Data Protection Regulations, ICH GCP and SOPs that cascade from the practices defined by the Academic and Clinical Central Office for Research and Development (ACCORD) SOPs.

Delegated research staff will enter the data required by the protocol into the eCRF following training in the definitions and methods used in completing the eCRF.

On completion of data collection, the Investigator must certify that the data entered into the eCRF is complete and accurate.

Data verification and cleaning will be performed as per ECTU local procedures and detailed in the Data Management Plan.

General laboratory data methods will be documented in laboratory notebooks and then analysed and written up for publication and dissemination to the scientific community. This lab data will act as the source data. All electronic data will be stored on secure personal computers and with rolling off-Site backup – the University of Edinburgh's central provision for this process (through ECTU). All data will be retained for 5 years in accordance with sponsor policy.

